## **14.8 PREMATURE DISCONTINUATION OF THE STUDY OR PREMATURE CLOSE-OUT OF A SITE**

### **14.8.1 By the Sponsor**

The Sponsor has the right to terminate the participation of either an individual site or the study at any time, for any reason, including but not limited to the following:

- The information on the product leads to doubt as to the benefit/risk ratio.
- Patient enrollment is unsatisfactory.
- The Investigator has received from the Sponsor all IMP, means and information necessary to perform the clinical trial and has not included any patient after a reasonable period of time mutually agreed upon.
- Non-compliance of the Investigator or Subinvestigator, delegated staff with any provision of the clinical trial protocol, and breach of the applicable laws and regulations or breach of the ICH GCP.
- The total number of patients is included earlier than expected.

In any case the Sponsor will notify the Investigator of its decision by written notice.

#### **14.8.2 By the Investigator**

The Investigator may terminate his/her participation upon thirty (30) days' prior written notice if the study site or the Investigator for any reason becomes unable to perform or complete the clinical trial.

In the event of premature discontinuation of the study or premature close-out of a site, for any reason whatsoever, the appropriate IRB/IEC and regulatory authorities should be informed according to applicable regulatory requirements.

#### **14.9 CLINICAL TRIAL RESULTS**

The Sponsor will be responsible for preparing a clinical study report and to provide a summary of study results to the Investigator.

#### **14.10 PUBLICATIONS AND COMMUNICATIONS**

The Investigator undertakes not to make any publication or release pertaining to the study and/or results of the study prior to the Sponsor's written consent, being understood that the Sponsor will not unreasonably withhold its approval.

As the study is being conducted at multiple sites, the Sponsor agrees that, consistent with scientific standards, a primary presentation or publication of the study results based on global study outcomes shall be sought. However, if no multicenter publication is submitted, underway or planned within twelve (12) months of the completion of this study at all sites, the Investigator shall have the right to publish or present independently the results of this study in agreement with other Investigators and stakeholders. The Investigator shall provide the Sponsor with a copy of any such presentation or publication for review and comment at least 30 days in advance of any presentation or submission for publication. In addition, if requested by the Sponsor, any presentation or submission for publication shall be delayed for a limited time, not to exceed 90 days, to allow for filing of a patent application or such other justified measures as the Sponsor deems appropriate to establish and preserve its proprietary rights.

The Investigator shall not use the name(s) of the Sponsor and/or its employees in advertising or promotional material or publication without the prior written consent of the Sponsor. The Sponsor shall not use the name(s) of the Investigator and/or the collaborators in advertising or promotional material or publication without having received his/her and/or their prior written consent(s).

The Sponsor has the right at any time to publish the results of the study.

## **15 CLINICAL TRIAL PROTOCOL AMENDMENTS**

All appendices attached hereto and referred to herein are made part of this clinical trial protocol.

The Investigator should not implement any deviation from, or changes of the clinical trial protocol without agreement by the Sponsor and prior review and documented approval/favorable opinion from the IRB/IEC of an amendment, except where necessary to eliminate an immediate hazard(s) to clinical trial patients, or when the change(s) involves only logistical or administrative aspects of the trial. Any change agreed upon will be recorded in writing, the written amendment will be signed by the Investigator and by the Sponsor and the signed amendment will be filed with this clinical trial protocol.

Any amendment to the clinical trial protocol requires written approval/favorable opinion by the IRB/IEC prior to its implementation, unless there are overriding safety reasons.

In some instances, an amendment may require a change to the informed consent form. The Investigator must receive an IRB/IEC approval/favorable opinion concerning the revised informed consent form prior to implementation of the change and patient signature should be re-collected if necessary.

## 17 APPENDICES

## Appendix A    Summary of TLC Diet for High Cholesterol

Total Fat	25% to 35% total
calories* Saturated fat*	<7% total calories
Polyunsaturated fat	up to 10% total calories
Monounsaturated fat	up to 20% total calories
Carbohydrates†	50% to 60% total calories*
Protein	~15% total calories
Cholesterol	<200 mg/day (5.172 mmol/day)
Plant Sterols	2 g
Soluble Fiber such as psyllium	10 g to 25 g

\* ATP III allows an increase of total fat to 35 percent of total calories and a reduction in carbohydrate to 50 percent for persons with the metabolic syndrome. Any increase in fat intake should be in the form of either polyunsaturated or monounsaturated fat. Trans fatty acids are another LDL-raising fat that should be kept at a low intake.

† Carbohydrate should derive predominantly from foods rich in complex carbohydrates including grains - especially whole grains - fruits, and vegetables.

**Appendix B WHO Criteria (Dutch Lipid Network clinical criteria) for diagnosis of Heterozygous Familial Hypercholesterolemia (heFH)**

Diagnostic Scoring for Heterozygous Familial Hypercholesterolemia			
Family history			
a	First degree relative with known premature (men <55 yrs, women <60 yrs) coronary and vascular disease. OR		1
b	First degree relative with known LDL-cholesterol >95th percentile for age and sex.		
and/or			
a	First degree relative with tendon xanthomata and/or arcus cornealis. OR		2
b	Children below 18 yrs. with LDL-cholesterol >95th percentile for age and sex.		
Clinical history			
a	Patient has premature (men <55 yrs, women <60 yrs) coronary artery disease		2
b	Patient has premature (men <55 yrs, women <60 yrs) cerebral or peripheral vascular disease.		1
Physical examination			
a	Tendon xanthomata		6
b	Arcus cornealis below the age of 45 yrs.		4
Laboratory analysis			
	mmol/L	mg/dL	
a	LDL-cholesterol >8.5	>325	8
b	LDL-cholesterol 6.5-8.4	251-325	5
c	LDL-cholesterol 5.0-6.4	190-250	3
d	LDL-cholesterol 4.0-4.9	155-190	1
Deoxyribonucleic acid (DNA)-analysis			
a	Functional mutation low-density lipoprotein receptor gene present		8
Diagnosis of heFH is:			
	Definite When	>8 points	
	Probable When	6-8 points	
	Possible When	3-5 points	

## **Appendix C    Simon Broome Register Diagnostic Criteria for Heterozygous Familial Hypercholesterolemia**

### **Definite familial hypercholesterolemia is defined as:**

- Total-C >6.7 mmol/L (260 mg/dL) or LDL cholesterol above 4.0 mmol/L (155 mg/dL) in a child <16 years or Total-C >7.5 mmol/L (290 mg/dL) or LDL cholesterol above 4.9 mmol/L (190 mg/dL) in an adult. (Levels either pre-treatment or highest on treatment).

PLUS

- Tendon xanthomas in patient, or in 1st degree relative (parent, sibling, child), or in 2nd degree relative (grandparent, uncle, aunt).

OR

- DNA-based evidence of an LDL receptor mutation or familial defective apo B-100.

### **Possible familial hypercholesterolemia is defined as:**

- Total-C >6.7 mmol/L (260 mg/dL) or LDL cholesterol above 4.0 mmol/L (155 mg/dL) in a child <16 years or Total-C >7.5 mmol/L (290 mg/dL) or LDL cholesterol above 4.9 mmol/L (190 mg/dL) in an adult. (Levels either pre-treatment or highest on treatment).

And at least one of the following:

- Family history of myocardial infarction below 50 years of age in 2nd degree relative or below 60 years of age in 1st degree relative.
- Family history of raised cholesterol >7.5 mmol/L (290 mg/dL) in adult 1st or 2nd degree relative or >6.7 mmol/L (260 mg/dL) in child or sibling under 16 years of age.

## **Appendix D The Stages of Heart Failure – NYHA classification**

Physicians often assess the stages of heart failure according to the New York Heart Association (NYHA) functional classification system. This system relates to symptoms to everyday activity and the patient's quality of life.

Class	Patient Symptoms
Class I (Normal)	No limitation of physical activity. Ordinary physical activity does not cause undue fatigue, palpitation, or dyspnea (shortness of breath).
Class II (Mild)	Slight limitation of physical activity. Comfortable at rest, but ordinary physical activity results in fatigue, palpitation, or dyspnea.
Class III (Moderate)	Marked limitation of physical activity. Comfortable at rest, but less than ordinary activity causes fatigue, palpitation, or dyspnea.
Class IV (Severe)	Unable to carry out any physical activity without discomfort. Symptoms of cardiac insufficiency at rest. If any physical activity is undertaken, discomfort is increased.

## Appendix E    Summary of Adverse Events reporting instructions at Sanofi

[figure not shown]
EVENT CATEGORY	REPORTING TIMEFRAME	SPECIFIC EVENTS IN THIS CATEGORY	CASE REPORT FORM COMPLETION		
			AE form	Safety complementary Form a	Other specific forms
Adverse event (non-SAE, non-AESI)	Routine	Any AE that is not SAE or AESI	Yes	No	No
Serious Adverse Event (non-AESI or AESI)	Expedited (within 24 hours)	Any AE meeting seriousness criterion per Section 10.4.1.2	Yes	Yes	No, unless applicable
Adverse Event of Special Interest (AESI)	Expedited (within 24 hours)	Pregnancy of female patient/subject (including male subject's partner as described in Section 10.4.1.3 )	Yes	Yes	Yes
		Symptomatic overdose with IMP	Yes	Yes	No
		Increase in ALT as follows: - ALT $\geq 3$ ULN (if baseline ALT <ULN) or - ALT $\geq 2$ times the baseline value (if baseline ALT $\geq$ ULN) Please refer to related flowchart (per Appendix C )	Yes	Yes	Yes
		Allergic drug reactions and/or local injection site reactions deemed to be allergic and requiring consultation with another physician as specified in Section 10.4.1.3 .	Yes	Yes	Yes b
		Neurologic events (requiring additional examinations/procedures and/or consultation with a specialist as specified in Section 10.4.1.3 )	Yes	Yes	Yes
		Neurocognitive events ( Section 10.4.1.3 )	Yes	Yes	Yes
		Non-allergic or allergic not requiring consultation with another physician, as described in Section 10.4.1.4 .	Yes	No	Yes b
Local injection site reaction	Routine				

EVENT CATEGORY	REPORTING TIMEFRAME	SPECIFIC EVENTS IN THIS CATEGORY	CASE REPORT FORM COMPLETION		
			AE form	Safety complementary Form a	Other specific forms
Laboratory or vital sign abnormality (non-SAE, non-AESI) that is: - Symptomatic - Requiring corrective treatment or consultation - Leading to IMP discontinuation or dose regimen modification	Routine	- Neutropenia - Thrombocytopenia - Acute renal insufficiency - Increase in CPK and suspicion of rhabdomyolysis Per Appendix C .	Yes	No	No

- a. Completion of a Safety Complementary Form is required for any AE meeting a seriousness or AESI criterion, even if this is not otherwise required according to the table for a particular type of AE
- b. General allergic reaction or local site reaction sections of the Complementary Form should be completed as applicable according to the type of reaction (general or local). However, for local injection site reactions that progress/expand/worsen/etc, both sections (local and general) of the Complementary Form should be completed.

## Appendix F General Guidance for the follow-up of laboratory abnormalities by Sanofi

### NEUTROPENIA

[figure not shown]

**Note:**

- The procedures described in the above flowchart are to be discussed with the patient only in case the event occurs. If applicable (according to local regulations), an additional consent (e.g., for HIV testing) will only be obtained in the case the event actually occurs.
- For individuals of African descent, the relevant value of concern is <1000/mm^3

Neutropenia is to be recorded as AE only if at least one of the criteria listed in Section 10.4.3 is met

## THROMBOCYTOPENIA

[figure not shown]

## INCREASE IN ALT

[figure not shown]
NOTE: ALT  $\geq$  3 ULN (if baseline ALT < ULN) or ALT  $\geq$  2 TIMES THE BASELINE VALUE (if baseline ALT  $\geq$  ULN) SHOULD BE NOTIFIED WITHIN 24 HOURS TO THE MONITORING TEAM (SEE Section 10.4.1.3, Section 10.4.4, and Section 10.4.5). IN ADDITION, IF ALT  $<$  3 ULN MEETS A SERIOUSNESS CRITERION, THE EVENT SHOULD BE NOTIFIED WITHIN 24 HOURS TO THE MONITORING TEAM

## ACUTE RENAL FAILURE

[figure not shown]
Acute renal failure is to be recorded as AE only if at least one of the criteria listed in Section 10.4.3 is met

[figure not shown]
## **SUSPICION OF RHABDOMYOLYSIS**

[figure not shown]

[figure not shown]
Suspicion of rhabdomyolysis is to be recorded as AE only if at least one of the criteria listed in Section 10.4.3 is met

[figure not shown]
## **Appendix G Self-injection Assessment Scale (SIAQ)**

[figure not shown]

[figure not shown]

[figure not shown]

## Appendix H Assessment of Local Injection Site Reactions

Local, Non- Allergic Reaction to Injectable Product	Mild (Grade 1)	Moderate (Grade 2)	Severe (Grade 3)	Very Severe (Grade 4)
Pain	Does not interfere with activity	Interferes with activity or repeated use of non-narcotic pain reliever	Prevents daily activity or repeated use of narcotic pain reliever	Emergency Room (ER) visit or hospitalization
Tenderness	Mild pain to touch	Pain with movement	Significant pain at rest	ER visit or hospitalization
Erythema / Redness *	2.5 – 5 cm	5.1 – 10 cm	>10 cm	Necrosis or exfoliative dermatitis
Swelling **	2.5 – 5 cm and does not interfere with activity	5.1 – 10 cm or interferes with activity	>10 cm or prevents daily activity	Necrosis
Itching	Does not interfere with activity	Interferes with activity or repeated use of topical or systemic treatment	Prevents daily activity or leads to other significant dermatologic conditions (such as infection, scarring, etc.)	Emergency Room (ER) visit or hospitalization
Other (Please specify)***	No modification of daily activities and/or does not require symptomatic treatment.	Hinders normal daily activities and/or requires symptomatic treatment.	Prevents daily activities and requires symptomatic treatment.	Emergency Room (ER) visit or hospitalization

\* In addition to grading the measured local reaction at the greatest single diameter, the measurement should be recorded as a continuous variable.

\*\* Swelling should be evaluated and graded using the functional scale as well as the actual measurement.

\*\*\* Please specify the other signs or symptoms (for example, hematoma, discoloration, reactivation, etc.).

ADAPTED from the toxicity grading scale table from the FDA Draft Guidance for Industry: Toxicity Grading Scale for Healthy Adult and Adolescent Volunteers Enrolled in Preventive Vaccine Clinical Trials April 2005.

## **Appendix I     Guidance on contraceptive methods for Denmark only**

The acceptable methods of contraception for female subjects included in this study in Denmark will include the following:

- Intra-uterine devices (IUD).
- Hormonal contraceptives (contraceptive pills, implants, transdermal patches, hormonal vaginal devices or injections with prolonged release).
- Subjects using a double-barrier contraceptive method (condom used with a diaphragm for example). However, this is limited to exceptional cases or conditions where the patient cannot use other contraceptive methods (ie, hormonal contraceptives or IUD).
- Subjects having a sterilized permanent partner may be allowed to participate.

The allowed methods of contraception can also be described in the patient's information (subject information leaflet).

## **Appendix J Guidance on contraceptive methods for Sweden only**

The acceptable methods of contraception for female subjects included in this study in Sweden will include the following:

Women of childbearing potential must use a highly-effective contraceptive method throughout the study treatment, and for 10 weeks after the last IMP injection for those patients who discontinue prematurely.

Below a list of contraceptive methods considered as highly-effective method for birth control:

- Oral (except low-dose gestagen (lynestrenol and norestisteron)), injectable, or implanted hormonal contraceptives.
- Intrauterine device.
- Intrauterine system (for example, progestin-releasing coil).
- Vasectomized male (with appropriate post-vasectomy documentation of the absence of sperm in the ejaculate) for 10 weeks after the last IMP injection for those patients who discontinue prematurely.

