## **6.2 DURATION OF STUDY PARTICIPATION**

### **6.2.1 Duration of study participation for each patient**

The study duration includes up to 3 weeks of screening period, a minimum of 12 weeks and up to a maximum 30 months of open label study treatment period and at least 2 weeks after the last alirocumab injection.

In each country, patient recruitment will end when alirocumab becomes commercially available (ie, accessible to the patient as per each country regulation) and reimbursed. In this case, study treatment can be switched to the commercial product (or another LMT) once the patient has completed the minimum of 12 weeks of study treatment.

The end of the study per patient is the last protocol planned visit or the resolution/stabilization of all SAEs and adverse event of special interest (AESI), or death, whichever comes last.

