**7.2.3 Exclusion criteria related to the current knowledge of Sanofi compound**

E 24. Known hypersensitivity to alirocumab or any component of the excipients.

E 25. Pregnant or breast-feeding women.

E 26. Women of childbearing potential not protected by highly-effective method(s) of birth control (as defined in the informed consent form and/or in a local protocol addendum) and/or who are unwilling or unable to be tested for pregnancy.

Note: Women of childbearing potential must have a confirmed negative pregnancy test at screening and inclusion visits. They must use an effective contraceptive method throughout the entire duration of the study treatment and for at least 10 weeks after the last study treatment injection. The applied methods of contraception have to meet the criteria for a highly effective method of birth control according to the “International Conference on Harmonisation of Technical Requirements for Registration of Pharmaceuticals for Human Use. M3 (R2): Guidance on nonclinical safety studies for the conduct of human clinical trials and marketing authorization for pharmaceuticals. ICH. 2009 Jun:1-25.”

Postmenopausal women must be amenorrheic for at least 12 months.

E 27. Male participant with a female partner of childbearing potential not protected by a highly-effective method(s) of birth control. See [Appendix K](#) (country-specific requirements).

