### **8.7.2 Contraception**

Women of childbearing potential must take an effective contraceptive method throughout the study treatment and during the 10-week period after the last study treatment injection. In some participating countries, specific contraceptive methods must be used by women of childbearing potential participating in a clinical trial (see Protocol [Appendix I](#) and [Appendix J](#)).

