**During the EOT/EOS visit the below will be performed:**

- Collect AEs.
- Check product complaints.
- Check compliance on IMP (review patient diary and treatment kit) and data collection on IMP administration.
- Record concomitant medication.
- Perform physical examination.
- Take vital signs including HR and BP.
- Laboratory tests: Hematology, Biochemistry, Liver panel (including Hepatitis C antibody, with reflexive testing if positive), Lipid profile, HbA1c. In case of abnormal results, a retest should be performed as soon as possible.
- Urinalysis (dipstick and if abnormal then microscopy).
- Urine pregnancy test (women of childbearing potential only).
- Document the end of treatment with collection of the following:
  - Last dose as per diary,
  - Reason for permanent treatment discontinuation,
  - Whether the patient switches to commercial alirocumab or to another therapy.
- Remind Nutritional Counseling (including reviewing patient's diet).
- IVRS/IWRS contact to register the patient's EOT/EOS.

Reminders:

- An appointment for lab sampling will be scheduled in case of any persistent laboratory abnormality at EOT/EOS visit.

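### Appendix J (Sweden) limits the 10-week post-injection contraception period to women who discontinue prematurely, while E 26 and Section 8.7.2 require it of every woman of childbearing potential

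*Protocol*

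**What the plan says.** Three places in the protocol set a contraception period after the last injection for women of childbearing potential.

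- **Section 7.2.3, E 26 (note):** contraception during study treatment and "for at least 10 weeks after the last study treatment injection". E 26 also refers to local text, "as defined in the informed consent form and/or in a local protocol addendum", but that phrase qualifies the highly effective methods, not the duration.
- **Section 8.7.2:** contraception during treatment and "during the 10-week period after the last study treatment injection". It then points to Appendices I and J, giving as the reason: "In some participating countries, specific contraceptive methods must be used by women of childbearing potential participating in a clinical trial".
- **Appendix J (Sweden only):** a highly effective method is mandatory during study treatment and "for 10 weeks after the last IMP injection for those patients who discontinue prematurely". The same condition is repeated in the bullet on vasectomized partners.

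The parallel Danish page, Appendix I, opens with "The acceptable methods of contraception for female subjects included in this study in Denmark will include the following". It lists methods and states no duration.

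**The concern.** Section 8.7.2 sends the reader to the country appendices for methods. Appendix J goes further: it restates the duration as an obligation and attaches a condition that the body text lacks. The natural reading is that a Swedish woman who finishes treatment as planned has no post-injection period to observe. Nothing in the protocol announces or justifies a shorter period for Sweden.

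The rule protects against fetal exposure. A Swedish site that counsels from the page written for its own country would err in the unsafe direction for such a woman. It would do so within the time when the protocol itself treats pregnancy as an adverse event of special interest.

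**Working it through.** The plan has no figure to reproduce here. The check is a comparison of texts with simple day counts.

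**1. Length of the period.** E 26 and Section 8.7.2: 10 weeks × 7 = 70 days after the last injection. Section 10.4.1.3 uses the same 70 days for reporting pregnancy as an AESI, for all patients and without regard to why treatment stopped.

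**2. The rule by type of exit, for a Swedish woman of childbearing potential.**

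| Exit | E 26 | Section 8.7.2 | Appendix J |
|---|---|---|---|
| Premature discontinuation | at least 70 days | 70 days | 70 days |
| Planned end of treatment | at least 70 days | 70 days | none stated |

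The texts agree on the length for the first row. In the second row the body text requires 70 days and Appendix J is silent.

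**3. Do planned exits without commercial alirocumab exist?** The protocol foresees two.

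- A switch to another lipid-modifying therapy. Section 6.2.1 says that "study treatment can be switched to the commercial product (or another LMT) once the patient has completed the minimum of 12 weeks" of treatment. The EOT/EOS visit (Section 10.1.2.5) records it: "Whether the patient switches to commercial alirocumab or to another therapy".
- Reaching the 30-month limit on open-label treatment (Section 6.1).

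**4. Could these count as premature discontinuation?** The protocol does not define the term. SAP Section 1.1 and footnote a to SAP Table 3 name patients who discontinue prematurely and patients who switch to another lipid-modifying therapy as two separate groups. Reaching a limit set by the protocol is not premature on any ordinary reading.

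**5. What remains after the last planned contact.** The EOT/EOS visit takes place 14 to 21 days after the last injection and includes the last scheduled pregnancy test. The part of the 70 days that follows it is:

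- visit at day 21: 70 − 21 = 49 days
- visit at day 14: 70 − 14 = 56 days

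In those 49 to 56 days no further visit is planned, so the woman depends mainly on the advice she has already been given.

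**6. Women who continue on commercial alirocumab.** E 26 and Section 8.7.2 still count from the last study injection, so the texts differ for them too. The practical effect is slight, because that injection does not end their exposure.

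**The case against.** The strongest reply is that this is silence, not contradiction. Appendix J does not say that planned completers may stop contraception. E 26 and Section 8.7.2 carry no Swedish exception, and a site that uses 10 weeks for everyone complies with every text. Section 8.7.2 also sets the duration before citing the appendices for methods, which suggests that the body text governs duration. This stands in part: the stricter rule does apply in Sweden, and the 70-day gap is between a stated period and an unstated one, not between two stated numbers. But Section 15 makes the appendices part of the protocol, no text says which wording prevails, and Appendix J phrases its duration as mandatory.

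A second reply is that a switch to another therapy might itself be premature discontinuation. Section 10.3.2 defines permanent discontinuation broadly, and the SAP passages that separate the two groups concern a follow-up visit under the original protocol, since removed. That leaves the switch arguable. The 30-month limit is the clearer case but has little reach: the first patient was enrolled on 08 July 2015 (SAP Section 1.5), 30 months later is January 2018, and Section 6.2.2 ends the study no later than the beginning of 2018. Only the earliest enrollees could reach the limit.

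Third, harm requires a site to overlook E 26 and Section 8.7.2 and to rely on the appendix alone, and the consent form may state the rule correctly. Both points are fair and limit the weight of the concern. They do not justify leaving a narrower safety rule on the page headed for Sweden.

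**Conclusion.** The concern holds. Appendix J states the post-injection period more narrowly than E 26 and Section 8.7.2. For a planned completer the difference is 70 days required against none stated; for a woman who discontinues prematurely, the texts give the same 10 weeks.

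The conclusion assumes that a site might use the Sweden page as its full rule, and that at least some planned exits are not premature discontinuation. The group concerned is narrow: Sweden, childbearing potential, planned exit, no commercial alirocumab. Its size is not in the documents, and the Swedish consent wording cannot be seen. This is a point of participant protection that should be corrected; it does not touch the statistical analysis.

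**What to change.** Make two edits in Appendix J.

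1. In the main sentence, delete the condition that limits the period to premature discontinuation and insert *at least* before the 10 weeks, so that it matches E 26.
2. In the bullet on vasectomized partners, remove the duration wording altogether, so that the main sentence sets the period for every listed method.

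Then check that the Swedish consent text gives the same period for all women of childbearing potential. The cost is the two edits and that check; no visit, test or data item is added.
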